5.1 Description

The study drug will come as a tablet that the participant will be advised to take once a day, preferably in the morning with a meal.

5.2 Treatment Regimen

Adolescents who received fluoxetine during the acute phase and were responders (CGI-I = much improved or very much improved (CGI-I = 1 or 2)) will continue their acute phase dosing regimen and will meet with the psychiatrist on a monthly basis.

Adolescents who received fluoxetine during the acute phase and were partial responders (CGI-I = minimally improved (CGI-I = 3)) will enter the continuation phase on 40mg fluoxetine, and will have their dose increased to 60mg. Partial responders will meet with the psychiatrist biweekly for the first 2 months and monthly for the second 2 months. Adolescents who received only IPT-A during acute phase and were partial responders (CGI-I = minimally improved (CGI-I = 3)) will begin treatment with fluoxetine during the continuation phase, in addition to continuing their IPT-A treatment. The dosage schedule will be 10mg per day for the first week and 20mg per day for the following 5 weeks. If no treatment response is observed by the 6th week, the dosage can be increased to 40mg per day. Pharmacotherapy sessions will be scheduled weekly for the first 4 weeks and biweekly thereafter. Pharmacotherapy sessions will include assessment of vital signs, adverse effects, safety, and symptomatic response.

CONFIDENTIAL

5.3 Method for Assigning Subjects to Treatment Groups

There is no randomization in this study. Assignment to treatment groups is described above (based on CGI-I score).

5.4 Preparation and Administration of Study Drug

The study psychiatrist will give the adolescent a prescription for the study medication that they will then fill with a licensed pharmacy.

5.5 Subject Compliance Monitoring

Adolescents will be given enough pills to last until their next scheduled appointment and will be asked to bring back the bottle of pills to each appointment. The study coordinator or the psychiatrist will count the number of pills remaining to assess treatment adherence. Families will be provided with the study pager number with instructions for emergencies during after hours. Families will be advised to call 911 in case of life threatening emergencies.

5.6 Prior and Concomitant Therapy

Adolescents will not be permitted to take any medications for a psychiatric diagnosis other than ADHD. Depressed adolescents with a comorbid diagnosis of ADHD who are on a stable dose of stimulant medication (> 3 months) will be eligible to participate in the studies. Adolescents will not be permitted to participate in alternative forms of psychotherapy (e.g. family therapy, group therapy, additional individual therapy).

5.7 Drug Supply

The psychiatrist will give the adolescent a prescription for the study medication that they will then fill with a licensed pharmacy. If the families' insurance company does not cover the cost of the medication, the family will need to pay for the medication out of pocket.

The following products are manufactured by Eli Lilly and Company for Dista Products Company: Pulvule are available in 10mg, 20mg and 40mg capsule strengths and packages as follows:

	Pulvule Strength		
	10 mg¹	20 mg¹	40 mg¹
Pulvule No.2	PU3104	PU3105	PU3107
Cap Color	Opaque green	Opaque green	Opaque green
Body Color	Opaque green	Opaque yellow	Opaque orange
Identification	DISTA 3104 Prozac 10 mg	DISTA 3105 Prozac 20 mg	DISTA 3107 Prozac 40 mg

CONFIDENTIAL

This material is the property of the University of Minnesota. Do not disclose or use except as authorized in writing by the study sponsor

6 Study Procedures

Continuation IPT-A. Adolescents who have responded to acute phase treatment (CGI-I = much improved or very much improved) will attend 4 biweekly IPT-A sessions followed by 2 monthly sessions. Adolescents who showed a partial response to acute phase treatment (CGI-I = minimally improved) will attend 8 weekly IPT-A sessions followed by 2 monthly sessions.

Continuation Pharmacotherapy. Adolescents who received fluoxetine during the acute phase and were responders (CGI-I = much improved or very much improved) will continue their acute phase dosing regimen and will meet with the psychiatrist on a monthly basis. Adolescents who received fluoxetine during the acute phase and were partial responders (CGI-I = minimally improved) will enter the continuation phase on 40mg fluoxetine, and will have their dose increased to 60mg. Partial responders will meet with the psychiatrist biweekly for the first 2 months and monthly for the second 2 months. Adolescents who received only IPT-A during acute phase and were partial responders (CGI-I = minimally improved) will begin treatment with fluoxetine during the continuation phase, in addition to continuing their IPT-A treatment. The dosage schedule will be 10mg per day for the first week and 20mg per day for the following 5 weeks. If no treatment response is observed by the 6th week, the dosage can be increased to 40mg per day. Pharmacotherapy sessions will be scheduled weekly for the first 4 weeks and biweekly thereafter.

Assessments. Adolescents will enter continuation treatment at week 16. Assessments will be conducted at week 24 and 32. The week 32 evaluation is already funded through the K23 study.

7 Statistical Plan

7.1 Sample Size Determination

Statistical experts warn against over-interpreting pilot data for estimating power and effect sizes for larger clinical trials.⁵¹ Consequently, the proposed research study does not aim to evaluate the efficacy of the adaptive treatment strategies. Rather, the sample size was determined by the study aims which are to demonstrate the feasibility and acceptability of implementing the adaptive treatment strategies. With these aims in mind, an intent-to-treat sample size of 30 was selected. A sample size of 30 will help ensure there are enough depressed adolescents in each adaptive treatment strategy to assess feasibility and acceptability.

7.2 Statistical Methods

All statistical analyses will be conducted on the intent-to-treat sample.

- Hypothesis 1: Among families in the acute phase study who are eligible to participate in continuation treatment, the percentage of adolescents and parents

CONFIDENTIAL

who consent to participate in the continuation treatment, and associated 95% confidence intervals will be calculated.

- Hypothesis 2: The mean/median (depending on the distribution) number and proportion of sessions attended by adolescents, as well as the associated 95% confidence intervals, will be calculated. The proportion of adolescents dropping out of treatment prematurely, and the associated 95% confidence interval, will be calculated.
- Hypothesis 3: An overall mean treatment satisfaction rating, and associated 95% confidence interval, will be calculated based on adolescents' and parents' responses on the CSQ-8.
- Hypothesis 4: An overall mean treatment satisfaction rating and the associated 95% confidence interval will be calculated based on clinicians' response on the clinician satisfaction measure.
- Hypotheses 5 & 6: (1) Primary analyses will examine within-subject change scores in CDRS, C-SSRS and CGAS over the course of acute and continuation treatment using repeated measures analysis of variance (ANOVA). Linear regression and analysis of covariance (ANCOVA) adjusting for pre-treatment scores will also be used to analyze changes in adolescents' outcomes. The magnitudes of changes in outcomes variables over time will be assessed using the paired t-test or Wilcoxon signed-rank test for continuous variables. Mixed-effects regression models will also be employed to compare CDRS, C-SSRS, and CGAS scores over multiple time points in order to obtain information on specific patterns of change over time. (2) Secondary analyses comparing within-subjects change scores across treatment groups on self-report measures of depression (BDI-II) and functioning (CBQ, SAS-SR) will be conducted using two-sample t-test, Wilcoxon rank sum test, and linear regression analysis. Hierarchical linear modeling (HLM) will also be conducted to compare scores over multiple time points within each treatment group. (3) Recovery will be defined as an absence of depression symptoms on the KSADS-PL for at least 8 weeks. Relapse will be defined as the reemergence of 5 or more symptoms of depression on the KSADS-PL. The percentage of adolescents who meet recovery criteria, and associated 95% confidence interval will be calculated. The percentage of adolescents who meet relapse criteria, and associated 95% confidence interval will be calculated. For those with a relapse, the mean (SD) time from recovery to relapse will be calculated.

Exploratory Analyses: Exploratory analyses will be conducted to determine whether comorbid psychiatric disorders, baseline severity of depression, and different forms of functioning (CBQ, SAS-SR, CGAS) predict or moderate positive or negative treatment outcomes. Potential predictors and moderators will be used to refine the personalized treatment strategy that will be tested in the subsequent R01.

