possible that adolescents seeking treatment from a community clinic might be at a greater risk for clinical deterioration and might be less likely to demonstrate a clinical improvement than if they received the treatments provided in this study. What is experimental in this study is the criteria for initiating a change in the treatment plan, the timing of a potential change in the treatment plan, and the type of change to the treatment plan. Currently, there are virtually no empirically-derived guidelines to direct clinicians in deciding whether, when, or how to alter a treatment plan for adolescent depression. Consequently, we expect the relation of the anticipated benefits to the risks to be at least as favorable to the subjects as that presented by available non-study treatment.

2 Study Objectives

Aim 1: Assess the feasibility and acceptability of the personalized continuation treatment strategy.

- Hypothesis 1: Adolescents who responded to the acute phase treatment provided in the K23 study and their parents will consent to participate in continuation treatment.
- Hypothesis 2: Adolescents will be adherent to continuation treatment and will complete the continuation treatment protocol.
- Hypothesis 3: Adolescents and parents will report satisfaction with continuation treatment.
- Hypothesis 4: Treating clinicians will report satisfaction with continuation treatment.

Aim 2: Estimate variances of primary and secondary outcomes with the continuation treatment.

- Hypothesis 5: Adolescents who were responders to acute treatment will show sustained response to continuation treatment.
- Hypothesis 6: Adolescents who were partial responders to acute treatment will show significant improvement in depressive symptoms and social and global functioning.

Aim 3: Conduct exploratory hypothesis-generating analyses to inform further development of the personalized continuation treatment strategy to be tested in a subsequent R01 proposal.

3 Study Design

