3.2 Primary Study Endpoints

The primary outcome measure is feasibility/acceptability (treatment satisfaction, session attendance, drop-out rates)

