4.4 Early Withdrawal of Subjects

4.4.1 When and How to Withdraw Subjects

A subject may be withdrawn from the study prior to expected completion for the following reasons:

- Participant or participant's parent(s) withdraw consent
- Participant fails to adhere to protocol requirements (no show to 3 appointments)

CONFIDENTIAL

This material is the property of the University of Minnesota. Do not disclose or use except as authorized in writing by the study sponsor

- Participant experiences adverse side effects to the fluoxetine that are intolerable to the adolescent or the parent.
- Participant experiences a significant worsening in symptoms: the participant will be evaluated by an independent safety monitor if at any time any of the following occur: 1) a suicide attempt, 2) serious suicidal ideation (with a plan and/or intent) and refusal to contract for safety, 3) psychiatric hospitalization, 4) possible need for psychiatric hospitalization, or 5) significant worsening of depressive or other clinical symptoms (CDRS-R > 76 or CGI improvement score > 5). Adolescents will be removed from the study immediately following review if the independent safety monitor deems that the patient requires treatment outside of study protocols or if the treatment provided in the study is contraindicated.

If a subject exits the study for any reason, the participant will be provided with referrals to receive treatment out of the protocol.

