4.4.2 Data Collection and Follow-up for Withdrawn Subjects

In the event of subject withdrawal from the treatment, we will ask permission to contact the family to continue to complete the study evaluations. Subjects will be determined lost to follow-up if they do not respond to 3 phone calls to their primary number.

5 Study Drug

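### Does the drop-out rate in Hypothesis 2 need a written case definition before it can be analysed?

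*Combined protocol and SAP*

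**What the plan says.** Section 3.2 sets the endpoint: "The primary outcome measure is feasibility/acceptability (treatment satisfaction, session attendance, drop-out rates". Hypothesis 2 in Section 2 reads: "Adolescents will be adherent to continuation treatment and will complete the continuation treatment protocol". The matching rule in Section 7.2 is: "The proportion of adolescents dropping out of treatment prematurely, and the associated 95% confidence interval, will be calculated". For attendance, Section 7.2 plans the number and the proportion of sessions attended, each with a 95% confidence interval, and it places every analysis on the intent-to-treat sample.

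Section 4.4.1 introduces its list of exits with "A subject may be withdrawn from the study prior to expected completion for the following reasons". The list covers withdrawn consent, "Participant fails to adhere to protocol requirements (no show to 3 appointments", "Participant experiences adverse side effects to the fluoxetine that are intolerable to the adolescent or the parent" and clinical worsening. For worsening, "Adolescents will be removed from the study immediately following review" applies if the independent safety monitor so decides. Section 4.4.2 uses a different term: "In the event of subject withdrawal from the treatment, we will ask permission to contact the family", so that evaluations can go on. It defines loss to follow-up separately, by three unanswered calls. Section 8.4 describes withdrawing the medication after an adverse reaction while staff follow the patient. None of these sections refers to Hypothesis 2.

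The Study Summary lists therapy session attendance and drop-out for each adaptive treatment strategy. Section 3.1 schedules the IPT-A sessions by response group.

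**The concern.** Drop-out is one of three components of the primary outcome, yet the plan describes several kinds of exit and does not say which ones Hypothesis 2 counts. It is unclear whether an adolescent removed on safety grounds has dropped out, or whether one who stops fluoxetine but keeps attending IPT-A has done so. Section 7.2 does give case definitions for recovery and relapse, which belong to Hypotheses 5 and 6, so the omission stands out. Two analysts could report different rates from the same data, and the choice might be made once the exits are known. The kinds of exit also mean different things: families leaving speaks to acceptability, and safety removals speak to clinical course.

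A smaller worry concerns attendance. Hypothesis 2 says only sessions, Section 3.1 also calls the medication visits sessions, and nothing says whether sessions falling after an exit count as missed.

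**Working it through.** The plan states no expected drop-out rate, precision target or feasibility threshold, so there is no figure of its own to reproduce. The check has three parts.

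**1. What the text already settles.** Inputs: Hypothesis 2 (Section 2), the 16-week course (Section 3.1), drop-out being from treatment and the intent-to-treat sample (Section 7.2). The complement of completing the protocol is stopping study treatment before it is completed. Applied to each exit:

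| Exit | Source | Plain reading |
|---|---|---|
| Consent withdrawn during treatment | 4.4.1 | Counts |
| Withdrawn after three no-shows | 4.4.1 | Counts; non-attendance is ordinary drop-out |
| Lost to follow-up during treatment | 4.4.2 | Counts |
| Leaves treatment, evaluations continue | 4.4.2 | Counts; the rate concerns treatment, not evaluations |
| Withdrawn for side effects, or removed after safety review | 4.4.1 | Counts as non-completion; arguable if drop-out is taken to mean the family's choice |
| Fluoxetine stopped, IPT-A continues | 8.4 | Open; treatment as a whole has not stopped |

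The last row is itself partly inferred. Section 8.4 does not say that IPT-A goes on after the medication is withdrawn, and Section 4.4.1 already lists intolerable side effects as a reason for leaving the study.

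**2. Size of what stays open.** Input: n = 30 (Section 7.1). One reclassified adolescent changes the rate by 1/30 = 3.3 points. Assumed exits, for illustration only: 2 consent withdrawals, 2 no-show withdrawals, 1 safety removal, 1 fluoxetine stop with IPT-A continuing. Exact (Clopper-Pearson) 95% intervals:

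- Family exits and no-shows only: (2 + 2)/30 = 4/30 = 13.3% (3.8% to 30.7%).
- All who stop study treatment (plain reading): (2 + 2 + 1)/30 = 5/30 = 16.7% (5.6% to 34.7%).
- Stopping one component also counted: (5 + 1)/30 = 6/30 = 20.0% (7.7% to 38.6%).

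The spread is 20.0 − 13.3 = 6.7 points. The interval at 5/30 is 34.7 − 5.6 = 29.1 points wide. A wider spread, starting from 2/30 = 6.7% (0.8% to 22.1%), arises only if adolescents withdrawn for three no-shows are not drop-outs, and nothing in the documents supports that.

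**3. Attendance.** Scheduled IPT-A sessions from Section 3.1: responders 4 + 2 = 6; partial responders 8 + 2 = 10. The Study Summary's reference to therapy sessions points to IPT-A, and the intent-to-treat statement points to all scheduled sessions as the denominator.

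That denominator matters. A partial responder who attends all 8 weekly sessions and then leaves scores 8/10 = 80% of scheduled sessions, or 8/8 = 100% of those offered before exit. If 6 of 30 leave at the midpoint after attending everything, the mean proportion is (24 + 6 × 0.5)/30 = 90%, against 100% if counting stops at exit. Keeping the whole sample and its whole schedule gives the 90%.

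The raw count does depend on case mix. With an assumed partial-responder share of 20% to 40%, full attendance averages 6 × 0.8 + 10 × 0.2 = 6.8 to 6 × 0.6 + 10 × 0.4 = 7.6 sessions. Section 7.2 already plans the proportion beside the count, and the proportion corrects for this.

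**The case for a change.** The strongest case for a change is that feasibility rates are the main product of this pilot. Section 7.1 sets the sample size by them, and Section 7.2 says exploratory findings will refine the strategy for a later trial. A primary component should not be left to inference when secondary events have definitions, and the wording about dropping out of treatment does not by itself settle safety removals or one-component stops. A definition would take a few lines and need no extra subjects or visits.

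Some of this stands. No sentence links the exits in Sections 4.4.1, 4.4.2 and 8.4 to Hypothesis 2, and a breakdown by reason would be informative. But the argument shows an unwritten detail, not a wrong method. The open cases are few, the natural reading gives a sound proportion, and no decision in the plan turns on the exact value. At this sample size a breakdown by reason is optional description: a single event, 1/30, has an exact 95% interval of 0.1% to 17.2%. That the choice would be shaped by the observed exits is possible, but the documents give no sign of it.

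**Conclusion.** The gap is real but minor, and the plan can stand. Followed as written, Hypothesis 2 yields the proportion of the intent-to-treat sample that stopped study treatment before completing the 16-week protocol, with a confidence interval. That is a valid descriptive estimate for an open-label, single-arm pilot without a comparison or threshold. What remains to judgement is whether a handful of adolescents with safety removals, side-effect withdrawals or fluoxetine-only stops are counted, at 3.3 points each. Under the assumed exits the range is 13.3% to 20.0%, well inside the sampling uncertainty. The attendance denominators of 6 and 10 follow from the schedule.

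The conclusion rests on reading drop-out as the complement of completing the protocol, and on the open cases being few. The exit counts and the partial-responder share used above are assumptions, not figures from the documents.

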Diagnosis and Main Inclusion Criteria	Male and female adolescents (ages 12-18) will be eligible for the study if they completed acute phase treatment and showed at least a partial response to treatment (CGI-I of minimally improved or better (CGI-I \leq 3)). Adolescents will enter continuation treatment having either received 12 sessions of IPT-A, 16 sessions of IPT-A, or 12 sessions of IPT-A plus fluoxetine.
Study Product, Dose, Route, Regimen	Adolescents who received fluoxetine during the acute phase and were responders (CGI-I = much improved or very much improved (CGI-I = 1 or 2)) will continue their acute phase dosing regimen and will meet with the psychiatrist on a monthly basis. Adolescents who received fluoxetine during the acute phase and were partial responders (CGI-I = minimally improved (CGI-I = 3)) will enter the continuation phase on 40mg fluoxetine, and will have their dose increased to 60mg. Adolescents who received only IPT-A during acute phase and were partial responders (CGI-I = minimally improved (CGI-I = 3)) will begin treatment with fluoxetine, in addition to continuing their IPT-A treatment. The dosage schedule will be 10mg per day for the first week and 20mg per day for the following 5 weeks. If no treatment response is observed by the 6th week, the dosage can be increased to 40mg per day.¹⁵
Duration of administration	16 weeks
Reference therapy	Interpersonal Psychotherapy for Depressed Adolescents (IPT-A)

CONFIDENTIAL

This material is the property of the University of Minnesota. Do not disclose or use except as authorized in writing by the study sponsor

Statistical Methodology	

1. Mean [95% confidence interval] treatment satisfaction for each adaptive treatment strategy (ATS)
2. Mean therapy session attendance and dropout rates for each ATS.
3. Within-subject change scores in CDRS-R, SAS-SR, and CGAS scores for the early and late decision point groups from pre- to post-treatment using repeated measures ANOVA.
----------------------------	--

CONFIDENTIAL

1 Introduction

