Continuation Pharmacotherapy. Adolescents who received fluoxetine during the acute phase and were responders (CGI-I = much improved or very much improved) will continue their acute phase dosing regimen and will meet with the psychiatrist on a monthly basis. Adolescents who received fluoxetine during the acute phase and were partial responders (CGI-I = minimally improved) will enter the continuation phase on 40mg fluoxetine, and will have their dose increased to 60mg.⁴⁰ Partial responders will meet with the psychiatrist biweekly for the first 2 months and monthly for the second 2 months. Adolescents who received only IPT-A during acute phase and were partial responders (CGI-I = minimally improved) will begin treatment with fluoxetine during the continuation phase, in addition to continuing their IPT-A treatment. The dosage schedule will be 10mg per day for the first week and 20mg per day for the following 5 weeks. If no treatment response is observed by the 6th week, the dosage can be increased to 40mg per day.⁴¹ Pharmacotherapy sessions will be scheduled weekly for the first 4 weeks and biweekly thereafter. Pharmacotherapy sessions will include assessment of vital signs, adverse effects, safety, and symptomatic response.

Assessments. Assessments will be administered by independent evaluators who are blind to treatment condition. Adolescents will enter continuation treatment at week 16. Assessments will be conducted at week 24 and 32. The week 32 evaluation is already funded through the K23 study. Assessment measures include the Schedule for Affective Disorders and Schizophrenia for School-aged Children-Present and Lifetime Version (K-SADS-PL),⁴² Children's Depression Rating Scale-Revised (CDRS-R),⁴³ Columbia Suicide Severity Rating Scale (CSSRS),⁴⁴ Global Assessment Scale for Children (C-GAS),⁴⁵ Beck Depression Inventory-II (BDI-II),⁴⁶ Social Adjustment Scale-Self-report (SAS-SR),⁴⁷ Conflict Behavior Questionnaire (CBQ),⁴⁸ and Client Satisfaction Questionnaire (CSQ-8).⁴⁹

CONFIDENTIAL

Treatment Phase	Acute	Continuation	
Assessment	Week 16	Week 24	Week 32

R = Responder (CGI-I = much improved or very much improved), PR = Partial Responder (CGI-I = minimally improved), NR = Nonresponder (CGI-I = no change or worsening)

CONFIDENTIAL

This material is the property of the University of Minnesota. Do not disclose or use except as authorized in writing by the study sponsor

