12.3 Subject Stipends or Payments

The adolescent will receive \$30 in cash directly after the week 24 evaluation and the parent will receive \$10 in cash for the week 24 evaluation.

13 Publication Plan

Neither the complete nor any part of the results of the study carried out under this protocol, nor any of the information provided by the sponsor for the purposes of performing the study, will be published or passed on to any third party without the consent of the study sponsor. Any investigator involved with this study is obligated to provide the sponsor with complete test results and all data derived from the study.

CONFIDENTIAL

This material is the property of the University of Minnesota. Do not disclose or use except as authorized in writing by the study sponsor

14 References

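### Hypothesis 3 concerns adolescents and parents, but Section 7.2 most naturally plans a single combined CSQ-8 mean, and no mean by informant is planned

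*Combined protocol and SAP*

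**What the plan says.** Hypothesis 3, under Aim 1 in Section 2, is that "Adolescents and parents will report satisfaction with continuation treatment". Section 3.2 places satisfaction in the primary outcome: "The primary outcome measure is feasibility/acceptability (treatment satisfaction, session attendance, drop-out rates").

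Section 7.2 gives the matching analysis: "An overall mean treatment satisfaction rating, and associated 95% confidence interval, will be calculated based on adolescents' and parents' responses on the CSQ-8". The next hypothesis, on treating clinicians, is handled in parallel: an overall mean with its interval "will be calculated based on clinicians' response on the clinician satisfaction measure".

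The Statistical Methodology row of the Study Summary lists a mean and 95% CI of "treatment satisfaction for each adaptive treatment strategy (ATS"), which splits by strategy and not by informant. Neither place sets a CSQ-8 level that would count as satisfied, and neither says how the two informants' answers are to be brought together.

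**The concern.** The hypothesis names two groups that can differ in their view of the same treatment. An adolescent attends the sessions and, where prescribed, takes the medication, while a parent judges from outside. If the plan yields one number from both, a satisfactory figure could arise because both groups were satisfied, or because one was well satisfied and the other was not. The analysis would then not answer its own hypothesis, on a component of the primary outcome. The sample size in Section 7.1 is also justified by feasibility and acceptability, so this is one of the results the pilot exists to produce.

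**Working it through.** The plan gives no figure to reproduce. Section 7.1 chooses 30 participants without a precision target, and no CSQ-8 standard deviation is stated. The check is therefore a reading of the text, followed by two short calculations in SD units.

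**1. What Section 7.2 plans.**
- Hypothesis 3 has one mean and the singular form of confidence interval.
- In the same list, Hypothesis 1 (consent of adolescents and parents) and the attendance part of Hypothesis 2 (number and proportion of sessions) use the plural. The single dropout proportion takes the singular. This favours reading Hypothesis 3 as one estimate.
- Hypothesis 4 uses overall for clinicians alone. There the word cannot mean combined across informants, so it does not prove the combined reading of Hypothesis 3.
- No other section plans a mean for adolescents or for parents alone.

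**2. What a combined mean can show.** Let A and P be the adolescent and parent means. With equal numbers the combined mean is C = (A + P)/2, so C − A = P − C = (P − A)/2. The combined mean is half the gap away from each group, whatever the size of the gap. Measured from the combined mean, these pairs all give the same C:
- A = 0, P = 0 (no gap)
- A = −0.5 SD, P = +0.5 SD (gap 1 SD)
- A = −0.75 SD, P = +0.75 SD (gap 1.5 SD)

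The gaps are illustrations, as the documents give none. The conclusion depends neither on their size or direction nor on how the interval is computed.

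**3. What separate reporting costs in precision.** Assume 30 respondents per informant, one parent per adolescent, equal SDs and within-family correlation ρ of 0.3 to 0.7. The sample size comes from Section 7.1; the rest is assumed. The t multiplier on 29 degrees of freedom is 2.045.
- One informant: 2.045/√30 = 0.373 SD.
- Mean of 30 family averages: 2.045 × √((1 + ρ)/60), which is 0.301 SD at ρ = 0.3, 0.323 SD at ρ = 0.5 and 0.344 SD at ρ = 0.7.
- Ratios: 0.373/0.301 = 1.24, 0.373/0.323 = 1.15 and 0.373/0.344 = 1.08.

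The interval for one informant is thus 24% to 8% wider than a correctly computed combined one.

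**The case against.** The best reply is that the text is ambiguous and the stakes are low. Overall may mean across strategies, in contrast to the Study Summary, or across questionnaire items, and the sentence never says that responses are pooled. The study is a non-randomised, open-label pilot with no satisfaction threshold. Attendance and dropout are analysed separately, and answers from both informants are planned, so the means could be split later. All of this stands, and it limits the weight of the point. It does not remove it: no wording commits to separate means, and the singular interval points the other way.

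Some stronger readings are tempting but not supported:
- A reader might infer that the interval will be too narrow because paired ratings are treated as independent. Section 7.2 does not say so. It leaves the unit of analysis and the visit unstated, which is missing detail and not an error.
- A reader might infer that unequal response will tilt a pooled mean towards one informant. Section 4.4.2 says "we will ask permission to contact the family to continue to complete the study evaluations". Permission is sought from the family, so a refusal would plausibly remove both informants together. The passage does not support an unequal split.
- A reader might infer from Section 12.3 ("in cash directly after the week 24 evaluation and the parent will receive" a smaller sum) that parents take part only at week 24. That section lists no week 32 payment for the adolescent either, and Section 3.1 notes that "The week 32 evaluation is already funded through the K23 study". The silence says nothing about parents at week 32.
- A reader might want a probability that the combined interval misleads about adolescents. Any such figure would rest on an assumed gap, direction and correlation, and no decision rule in the plan uses the interval in that way.

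**Conclusion.** The point holds as a modest improvement. On the most natural reading of Section 7.2, the satisfaction estimate cannot show whether each group named in Hypothesis 3 was satisfied, because with equal numbers it sits half of any gap from each group's mean. That result is algebraic and needs no assumption about the data. It does depend on the combined reading, which is likely but not certain. If the sponsor always meant one mean per informant, the plan needs only to say so. The precision figures rest on the assumptions listed with them. No test or decision rule is affected; the benefit is that the satisfaction estimates to be reported are fixed before the data are seen.

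**What to change.** In Section 7.2, under Hypothesis 3, state that the mean CSQ-8 rating and its 95% CI will be reported separately for adolescents and for parents, with the number responding in each group. If a combined mean is kept, label it supplementary and compute both it and its interval at family level, by averaging within families or with a family random effect. The same sentence can name the visit used.

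The cost is a change of wording and one more table row. Section 7.2 already plans CSQ-8 responses from both informants, so no new data are needed. The price is the wider interval: about 0.37 SD per informant with 30 respondents, against 0.30 to 0.34 SD for the family-level combined mean under the stated assumptions. With only 20 respondents in a group it would be 2.093/√20 = 0.47 SD.
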